4.5.2 Secondary Outcomes and Other Data

Change from baseline in COVID-19 Vaccine Confidence. Additional analysis of the VCI data will include the proportion of positive VCI responses at subsequent evaluations and the individual change in VCI between baseline and each follow-up evaluation. Subdomains of the VCI will be evaluated separately from the composite score.

Likelihood of recommending (promoting) COVID-19 vaccination. Adapted Net Promoter Score (NPS) questions⁵⁰ will assess the likelihood that participants would recommend 1) COVID-19 vaccination to others who are unvaccinated, and 2) COVID-19 booster vaccination to a coworker. Similar questions have been recommended previously^{51,52}. We will adopt the traditional scoring approach that categorizes respondents as promoters, passives, or detractors.

COVID-19 vaccine uptake and intent. We will assess uptake of the COVID-19 vaccines (any dose, initial series completion, and booster completion) using four questions that we developed. For those who report not being vaccinated or boosted, intent to get a COVID-19 vaccine (initial series or booster) will be assessed using two questions broadly adapted from prior work⁵³. All participants will also be asked if they would get regular vaccines in the future if they are recommended, using a single question.

Feeling informed about the COVID-19 vaccines. We will assess the degree to which participants' feel informed about the COVID-19 vaccines (have enough information and understand that information), using two self-developed questions. Our operational definition of feeling informed was influenced by the Decision Self-Efficacy Scale⁵⁴.

Identification of COVID-19 vaccine information and misinformation. We will assess participants' identification of COVID-19 vaccine-related information and misinformation, using four questions that were shown to have low rates of correct identification in the pre-launch survey data (see 4.1.2). Some questions were self-developed and some were adapted from prior work⁴³.

Trust in COVID-19 information from different sources. We will assess participants' trust in COVID-19 information provided by different people and organizations, using three items broadly adapted from prior work⁵⁵.

Change from baseline in secondary outcomes. Additional analysis of secondary outcomes will include their assessment at subsequent evaluations and the individual change in secondary outcomes between baseline and each follow-up evaluation.

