As-treated analysis of primary and secondary outcomes. Primary and secondary outcomes will also be assessed amongst participants who were exposed to their relevant primary study intervention.

Contextual factors. We will identify contextual factors that may contribute to COVID-19 vaccine intentions and decisions, including personal COVID-19 and vaccine experiences and participation in other COVID-19 vaccine research, using a single self-developed question.

External contextual factors. Outside of the study surveys and throughout the trial, we will monitor external factors that may impact participants' views and actions towards the COVID-19 vaccines. This may include monitoring policy and mandate changes for LTCWs and changes in the nature of the pandemic, among other things.

Participant characteristics. We will assess several participant characteristics including age, gender (adapted from^{56,57}), zip code, educational attainment (adapted from⁵⁸), race and ethnicity (adapted from⁵⁸), health insurance (adapted from^{58,59}), health literacy^{60,61}, religiosity⁶², LTCW role, duration of experience in long-term care, extent influenced by others regarding COVID-19 vaccination, and baseline vaccination status.

Intervention engagement. We will monitor the extent to which participants engage with their assigned primary and refresher intervention content. We will collect online activity data (i.e., social media website user history, webinar attendance records, email click rates) and participant self-reported engagement data via surveys. We will prioritize the use of online activity data to minimize potential measurement error³⁶. However, survey questions may be used where online activity data is not available or is incomplete; for example, to determine engagement with the webinar refresher recording (adapted from³⁶) and enhanced usual practice information. Data on engagement will be used to inform secondary trial analyses, as well as Aim 3.

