4.6 Sample Size and Power Calculation

Using historical Vaccine Confidence Index (VCI) data⁷⁰ and current vaccination rates⁷¹, a VCI threshold was determined that was significantly correlated with rates of vaccination ($p=0.0001$). Assuming the analytic approaches outlined in sections 4.7.2 and later, the sample size of 1,800

LTCWs (600 per arm) provides 80% power to detect an 8% difference in the rate of scores above this threshold between groups with a two-sided test at type I error rate of 0.05. The sample size is sufficient to retain 80% power to detect a 10% difference (assuming outcomes are randomly distributed across retained and lost subjects) after 40% attrition.

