- *Likelihood of recommending COVID-19 vaccination (others not vaccinated)*. This question will be evaluated using a Net Promoter Score (NPS) approach, adding one for each positive response, zero for neutral, and subtracting one for each negative response, then dividing by the number of non-missing responses for each trial arm. NPS values will be compared using Wald intervals [1].
- *Likelihood of recommending COVID-19 booster vaccination (coworker)*. This question will be evaluated using the NPS approach, described above.
- *COVID-19 vaccine uptake (any dose)*. This will be evaluated as a binary classifier compared across trial arms using two-proportion z-tests.
- *COVID-19 vaccine uptake (initial series completion)*. For participants who have received any dose of a COVID-19 vaccine, this will be evaluated as a binary classifier compared across trial arms using two-proportion z-tests.
- *COVID-19 vaccine uptake (booster completion)*. For participants who have completed their initial vaccine series, this will be evaluated as a three category variable (No, Not sure, Yes) compared across trial arms using chi-squared tests.
- *COVID-19 vaccine intent (initial series)*. For participants who are unvaccinated, we will assess their intentions of getting a COVID-19 vaccine, this will be evaluated using the Net Promoter Score approach, where the three responses – Yes, Not Sure, No – will be evaluated as analogous to promoter, neutral, and detractor, respectively. The question will be evaluated using the NPS analysis, described above.
- *COVID-19 vaccine intent (booster)*. For participants who have completed an initial vaccine series, this will be evaluated using the Net Promoter Score approach, where the three responses – Yes, Not Sure, No – will be evaluated as analogous to promoter, neutral, and detractor, respectively. The question will be evaluated using the NPS analysis, described above.
- *COVID-19 vaccine intent (future vaccine recommendations)*. Participants' intent to get COVID-19 vaccines regularly in the future if they are recommended will be evaluated using the Net Promoter Score approach, where the three responses – Yes, Not Sure, No – will be evaluated as analogous to promoter, neutral, and detractor, respectively. The question will be evaluated using the NPS analysis, described above.

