- *Feeling informed about the COVID-19 vaccines*. The degree to which participants' feel informed about the COVID-19 vaccines (have enough information and understand that information) will be evaluated using a continuous variable, calculated as the mean scale

score across two items ((1) having enough information, (2) understanding the information) for each participant. The mean of all mean scores will be compared across trial arms with two-sample unpaired t-tests.

- *Identification of COVID-19 vaccine information and misinformation.* Subjects' identification of COVID-19 vaccine information and misinformation will be scored on a scale of zero to four and treated as a continuous linear variable. Results will be compared across trial arms with two sample unpaired t-tests.
- *Trust in COVID-19 information from different sources.* Subjects' trust in COVID-19 information from different sources will be evaluated using a continuous variable, calculated as the mean scale score across three items for each participant. The mean of all mean scores will be compared across trial arms with two-sample unpaired t-tests.
- *Change from baseline in secondary outcomes.* Change from baseline will be scored as a binary variable with an increased value scored as one and a no change or decreased value scored as zero. For each evaluation after baseline, each arm will be compared using two-proportion z-tests. For vaccine and booster intent questions, where the intent question is not repeated if the participant indicates an increase in vaccination status, intent will be imputed from uptake. To be clear, an individual who is unvaccinated at T0, then returns at T1 and indicates that he or she is now vaccinated, will be presented with the vaccine intent question at T0 but not at T1. Because the individual is now vaccinated, asking about vaccine intent at T1 would be confusing. For analyzing change in vaccine intent, the individual whose vaccine status increases would be considered to have positive intent at T1. A similar approach will be used for booster intent.
- *As treated analysis of primary and secondary outcomes.* Primary and secondary outcome analyses will be repeated, limited to the as treated samples.

Aim 2

To determine if LTCWs' characteristics and other factors mediate and moderate the interventions' impact on vaccine confidence and other secondary outcomes.

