Change from baseline in COVID-19 Vaccine Confidence. Looking deeper at the change in vaccine confidence, analyses will consider (a) the proportion of positive (agree and strongly agree) responses in the VCI, (b) positive responses in each of the three VCI questions. Significant correlates with demographic, contextual, and study variables will be evaluated.

External contextual factors. Outside of the study surveys and throughout the trial, we will monitor external factors that may impact participants' views and actions towards the COVID-19 vaccines. This may include monitoring policy and mandate changes for LTCWs and changes in the nature of the pandemic, among other things.

Additional analyses. Any unvalidated thresholds utilized in the primary or secondary analyses will be evaluated for sensitivity to the choice of threshold in ROC analyses. Nonlinear higher-dimensional effects and interactions among variables will be identified by identifying positive or negative outcomes grouped around specific baseline characteristics that are highly unlikely to result from random chance.

Duplicate and missing data

Participants must complete a baseline (T0) survey to be considered enrolled in the study. In the event of duplicate complete T0 submissions, the first complete survey will be used. For participants who complete duplicate follow-up surveys (T1, T2 or T3), the first complete survey

will also be used. In order to be included in primary and secondary outcome analyses, participants must have valid primary outcome data at both T0 and T1.

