The study team will endeavor to minimize missing data; however, it is possible that efforts to ensure complete data collection within the response windows will be unsuccessful or because participants may choose not to respond to one or more questions. Should any primary and/or secondary outcome variables have >5% missing data, the reasons for any missing data will be considered through an analysis for common baseline characteristics of individuals with specific responses missing, those who were lost to follow-up, and those who did not respond to one or more evaluations but were not lost to follow-up. Specific questions with significantly higher rates of missing data will be reviewed for wording bias or missing response options. Based on these considerations, a stochastic outcome set model will be created using multiple imputation and Bayesian methods, as appropriate, to provide a high confidence range for imputed values. Using this approach, an expected result and confidence intervals will be produced for the missing data and the resulting analysis of the full data set, taking into account the statistical uncertainty attributed to the missing data. If available, data from both baseline and subsequent follow-up evaluations will be used in imputing missing results (e.g., responses from T0 and T2 evaluations could be used to impute T1 responses) through multiple imputation regression modeling [3].

Response rates and the frequency of missing data in the ITT and as-treated populations will be reported with the results.

Fraudulent enrollment

Identity verification of some participants will occur after they have completed their journey in the study (using TransUnion's TLOxp verification service). We will also conduct a rigorous review of survey metadata (e.g., IP addresses) and other responses to identify duplicate survey completions or other suspicious survey activity [4,5]. Upon discovery of compelling evidence of fraudulent or illegitimate enrollment, such subjects will be excluded from the study prior to any outcome analyses.

Methods to minimize bias

A naïve analysis will be conducted at the end of the study based only on the unmodified data reflecting ITT assignments of eligible subjects to establish an initial estimator. All primary and secondary analyses will be conducted based on the statistical analysis plan. The statistician member of the DSMB will also independently replicate primary study analyses to confirm their validity.

Multiple testing

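### Any-dose uptake cannot reverse, yet Appendix B drops or regression-imputes T1 answers that T0 or later surveys already fix; the main cost is precision

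*Combined protocol and SAP*

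**What the plan says.** - **Outcome.** For any-dose uptake, Appendix B (Secondary outcomes) states: "This will be evaluated as a binary classifier compared across trial arms using two-proportion z-tests". Series completion is analysed only among people with any dose, and booster completion only among series completers, with Not sure as a third answer category beside No and Yes.
- **Status at other visits.** Section 4.5.2 lists among the participant characteristics "extent influenced by others regarding COVID-19 vaccination, and baseline vaccination status". It also says "Additional analysis of secondary outcomes will include their assessment at subsequent evaluations", so status at T2 and T3 is available for those who return.
- **Inclusion rule.** For primary and secondary analyses alike, Appendix B (Duplicate and missing data) says "participants must have valid primary outcome data at both T0 and T1". The primary outcome is the Vaccine Confidence Index (VCI), not uptake.
- **Imputation rule.** The following paragraph applies when an outcome has more than 5% missing. It plans multiple imputation and Bayesian methods where suitable, leading to an analysis of the full data set. Where available, "data from both baseline and subsequent follow-up evaluations will be used in imputing missing results". It states no rule that a vaccinated person stays vaccinated.
- **The one logical fill.** For change in intent, when a participant's vaccination status has risen, "intent will be imputed from uptake". Nothing similar is written for uptake itself.
- **Attrition.** Section 4.6 considers power under a 40% loss, with outcomes assumed to be unrelated to who is lost.

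**The concern.** A missing attitude score is unknown. A missing any-dose answer often is not: Yes at T0 implies Yes at T1, and No at T2 or T3 implies No at T1. The plan accepts this kind of reasoning for intent but treats a missing uptake answer like a missing opinion.

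Two things are at stake. First, the inclusion rule discards people whose uptake is known, which widens the error bars. It also lets differences in survey response change the mix of vaccinated and unvaccinated people in each arm. Second, the inclusion and imputation paragraphs give different answers for a person with no T1 survey: one excludes them, the other imputes them. The analyst cannot tell which applies, and the cost for uptake depends on it.

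**Working it through.** **The plan's own figure.** The documents give no precision or missing-data figure for uptake. The nearest is the power statement for the primary outcome in section 4.6: 80% for 8 points, 600 per arm, two-sided 0.05. With pooled variance, power is 0.792 at 46% vs 54% (least favourable) and 0.834 at 30% vs 38%, so it reproduces.

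**Inputs.** From the documents: 600 per arm and the 40% attrition scenario (720 of 1,800 missing, 360 per arm left). Assumed, because the documents give no value: share vaccinated at T0 (v0), 50% to 95%; share of T1 non-responders who answer at T2 or T3 (r), 0 to 0.5; share of T0-unvaccinated people vaccinated by then (c), 0.05 to 0.15. The worked example uses v0 = 0.90 and 5% of the rest vaccinated by T1, so true uptake is 0.90 + 0.10 × 0.05 = 0.905.

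**1. How much is already known.** Carrying T0 Yes forward leaves 0.40 × (1 − v0) unknown: 12% at v0 = 0.70, 4% at 0.90, 2% at 0.95. Adding later No answers, the fixed share of missing values is v0 + (1 − v0) × r × (1 − c).
- Low end: 0.50 + 0 = 50%, or 360 of 720.
- High end: 0.95 + 0.05 × 0.5 × 0.95 = 97%, or 701 of 720.

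**2. Precision.**
- Complete cases: √(2 × 0.905 × 0.095 / 360) = 0.0219, about 2.2 points.
- All 600 known: √(2 × 0.905 × 0.095 / 600) = 0.0169.
- T0 Yes filled, the rest estimated from the 36 T0-unvaccinated responders per arm (600 × 0.10 × 0.60): variance per arm = 0.95² × 0.09/600 + 0.10² × 0.0475/36 = 0.0001354 + 0.0000132 = 0.0001486. The SE is √(2 × 0.0001486) = 0.0172, about 1.7 points.

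**3. Bias from dropping people.** Suppose there is no true difference. T0-vaccinated people respond at 60% in both arms, and T0-unvaccinated people at 60% in one arm and 40% in the other.
- First arm: 0.905.
- Second arm: (0.54 + 0.04 × 0.05) / (0.54 + 0.04) = 0.542/0.58 = 0.9345.
- False difference: 2.9 points.

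With the fill, and imputation within T0 status and arm, it is 0, provided non-response is unrelated to T1 uptake within those groups.

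**4. A partial repair that would not work.** Suppose only logically known values were exempted from the inclusion rule, T1 missingness were 30% in one arm and 50% in the other, and no later No answers were available. All T0-vaccinated people then enter, but only the responding T0-unvaccinated do.
- 30% missing: (0.90 + 0.07 × 0.05)/0.97 = 0.9314.
- 50% missing: (0.90 + 0.05 × 0.05)/0.95 = 0.9500.
- False difference: 1.9 points, again with no true difference.

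**5. Impossible imputed values.** This was simulated with 1,800 people, v0 of 0.70 or 0.90, 40% missing at T1, 30% of those returning at T2, and Bayesian logistic draws with ridge stabilisation.
- With T0 uptake, or T0 and T2 uptake, in the model, about 0.2% to 2% of missing T0-vaccinated people were drawn as No (roughly 1 to 10 of 504 to 648).
- Among people known to be unvaccinated at T2, 0.7% to 5% were drawn as Yes at T1 with T0 and T2 in the model, and 8% to 17% with T0 alone.
- With T0 uptake left out, 9% to 27% of the missing T0-vaccinated were drawn as No, so the model should name it.

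**The case against.** The strongest reply is that the imputation paragraph, carried out competently, already does most of the job. It points to baseline and later data, and its wording leaves room for a constraint. In a check at 90% vaccinated and 40% missing, lightly stabilised fits gave uptake of 90.4% to 90.5% against a true 90.5%. This stands, and it is why impossible values are treated here as minor.

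A reader might go further and infer that the plan would turn a large share of vaccinated people into unvaccinated ones, because T0 Yes predicts T1 Yes perfectly and a plain logistic model then has no finite coefficient. Drawing from such a fit does give nonsense, but Appendix B does not specify it and an analyst would see the failure at once.

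Three further limits also stand. The inclusion rule turns on missing VCI, so someone with T1 VCI data and a blank uptake item is kept. The 40% is a power scenario, not a projected non-response rate for the three-week survey. The arithmetic covers any-dose uptake only: eligibility admits people because they lack a booster, and a booster answer of Not sure fixes nothing, so it is not shown that most missing booster or series values are known.

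The reply does not rescue the inclusion rule. As written, it excludes people whose any-dose status is known, whatever the imputation model could have done.

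**Conclusion.** The point holds for any-dose uptake. The main harm comes from the inclusion rule: an SE of about 2.2 points instead of 1.7, and a possible bias if response depends on baseline vaccination status differently by arm (2.9 points in the scenario shown). Both figures rest on an assumed 90% vaccinated at T0 and 40% missing at T1; the bias also needs the assumed 60% vs 40% response split. Less missingness would shrink them. The absence of a constraint in the imputation model is a small, untidy defect, not a source of serious error under a usable fit.

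The uptake outcomes are secondary and carry no significance threshold (Appendix B, Multiple testing), so the primary result is unaffected. The change should be made because it is cheap and uses data already collected.

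**What to change.** In Appendix B, Duplicate and missing data:

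1. For the uptake outcomes, replace the T1 VCI requirement with all randomised participants who have T0 data. Do not limit the set to people whose status is logically known, since leaving out the unknown T0-unvaccinated biases the comparison (step 4 of the working).
2. Before counting missingness or imputing, carry an earlier any-dose Yes forward and a later No back.
3. Impute only what remains unknown, with T0 and later uptake in the model and under the same constraint.
4. Apply the logic to series completion and booster only where a definite Yes or No fixes the value.
5. Reconcile the inclusion and imputation paragraphs for every outcome, so that it is clear whether a person without T1 VCI data is excluded or imputed.

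The cost is a few sentences in the SAP and a few lines of code, with no new data. The downside is reliance on self-reported status, so contradictory answers across visits should be counted and reported. The values that remain unknown still rest on an untestable missing-data assumption, but for far fewer people.

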3.2 Aims and Objectives

Specific Aim 1: To compare the impact of two interventions delivered online: 1) a dialogue-based webinar using the existing COVID-19 Option Grid conversation aid and, 2) an interactive, dynamic, and multi-component social media website, compared to enhanced usual practice (link to Centers for Disease Control (CDC) vaccine website), on COVID-19 vaccine confidence (primary outcome), and other secondary outcomes among LTCWs (see Figure 1).

Hypothesis 1: Each intervention will be superior to enhanced usual practice at increasing vaccine confidence.

Hypothesis 2: The dialogue-based webinar intervention will be superior to the social media arm at increasing vaccine confidence.

We predict superiority of the dialogue-based webinar intervention based on stronger evidence that exists for dialogue-based approaches and SDM for improving vaccine hesitancy and/or uptake, as compared to social media approaches. While our social media website intervention includes elements of dialogue, this component is more explicit in the webinar intervention (see 'Interventions and control').

Specific Aim 2: To determine if LTCWs' characteristics and other factors mediate and moderate the interventions' impact on vaccine confidence and other secondary outcomes (See Figure 1).

Hypothesis 1: Increased perceptions of feeling informed about the vaccines, identification of vaccine information and misinformation, and trust in vaccine information provided by different sources will explain (mediate) the relationship between the interventions and vaccine confidence, as well as other secondary outcomes.

[figure not shown]
Exploratory: We will conduct exploratory heterogeneity of treatment effects (HTE) analyses to identify whether certain participant characteristics and beliefs moderate the relationship between the interventions and vaccine confidence, as well as other secondary outcomes.

Variables to be explored will include, but are not limited to, vaccination status, religious beliefs, perceived influence of others, age, race, ethnicity and personal experiences with COVID-19.

Specific Aim 3: To explore the implementation characteristics, contexts, and processes needed to sustain and scale up the use of interventions designed to increase vaccine confidence among LTCWs.

Hypothesis 1: Co-developing and adapting the implementation strategy and outcomes with LTCWs and other stakeholders will facilitate implementation.

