P-values ≥ 0.0001 will be reported to 4 decimal places; p-values less than 0.0001 will be reported as " <0.0001 ". The mean, standard deviation, and any other statistics other than quantiles, will be reported to one decimal place greater than the original data. Quantiles, such as median, minimum, or maximum will use the same number of decimal places as the original data. Estimated parameters, not on the same scale as raw observations (e.g. regression coefficients) will be reported to 3 significant figures.

Adherence to interventions

Analysis of both intention-to-treat (ITT) and as-treated populations will be performed. All participants who are randomized to a trial arm will be included in the ITT analyses. Participants who adhere to major engagement criteria for their primary intervention will be included in the as-treated analyses.

Analysis methodology

Aim 1

To compare the impact of two interventions delivered online: 1) a dialogue-based webinar (webinar) using the existing COVID-19 Option Grid conversation aid and, 2) an interactive and, dynamic, and multi-component social media web application (social media website), compared to enhanced usual practice (link to Centers for Disease Control (CDC) vaccine website), on COVID-19 vaccine confidence (primary outcome), and other secondary outcomes among LTCWs. We hypothesize that each intervention will be superior to enhanced usual practice at increasing vaccine confidence (*Hypothesis 1.1*) and that the dialogue-based webinar intervention will be superior to the social media arm at increasing vaccine confidence (*Hypothesis 1.2*).

Corresponding analyses

Primary outcome

The primary outcome is the binary classifier of vaccine confidence derived from the three-item Vaccine Confidence Index (VCI), evaluated at 3 weeks post-randomization, which will be analyzed by randomization arm. The determined binary predictors of intervention outcomes will be compared using two-proportion z-tests to identify significant differences between each intervention and enhanced usual practice (Arm 1 vs Arm 3 & Arm 2 vs Arm 3 - superiority analyses) and between the intervention arms (Arm 1 vs Arm 2 - two-tailed equivalency analysis).

Secondary outcomes

- *Change from baseline in COVID-19 Vaccine Confidence.* Analysis of change from

baseline will be based on a binary classifier whether the average score increases (1) or does not increase (2) at T1, T2, and T3 versus baseline.

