The primary outcome involves three separate tests, one a two-tailed equivalence test and two one-tailed superiority tests. In order to achieve a family-wise error rate less than 0.050, the Bonferroni method was employed to set a p-value threshold at 0.016 for each of the three primary outcome analyses. For each comparison, mean-value separation will be considered significant based on a 98.4% confidence interval, which translates to +/- 2.45 times the standard

error for the sample mean for the equivalence test and greater than 2.15 times the standard error for the superiority analyses.

Based on the high number of secondary outcome analyses (cross-sectional T1; change from baseline; ITT; as-treated), results data for these outcomes will be viewed in more aggregate form as trending in one direction or not, rather than adopting a specific Bonferroni-corrected p-value threshold.

References

1. B. Rocks, Interval Estimation for the “Net Promoter Score.” *Am. Stat.* 70, 365–372 (2016).
2. R. M. Baron, D. A. Kenny, The moderator–mediator variable distinction in social psychological research: Conceptual, strategic, and statistical considerations. *J. Pers. Soc. Psychol.* 51, 1173–1182 (1986).
3. T.E. Raghunathan, J.M. Lepkowski, J. Van Hoewyk, P. Solenberger, et al. A multivariate technique for multiply imputing missing values using a sequence of regression models. *Surv. Methodol.* 27, 85–96 (2001).

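### The three primary tests keep a fixed Bonferroni cut of 0.016. This is valid, but Holm's step-down rule gives the same error control with modestly more power for the second and third claims.

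*Combined protocol and SAP*

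**What the plan says.** Appendix B, under multiple testing, describes the family: "The primary outcome involves three separate tests, one a two-tailed equivalence test and two one-tailed superiority tests". The aim is stated as "In order to achieve a family-wise error rate less than 0.050", and for this "the Bonferroni method was employed to set a p-value threshold at 0.016 for each of the three primary outcome analyses". Decisions are read from intervals: "mean-value separation will be considered significant based on a 98.4% confidence interval, which translates to +/- 2.45 times the standard", continuing "error for the sample mean for the equivalence test and greater than 2.15 times the standard error for the superiority analyses". The arms are "compared using two-proportion z-tests to identify significant differences between each intervention and enhanced usual practice", and the two interventions are compared with each other by the same kind of test. The documents contain no step-down, ordered or gatekeeping rule for these tests.

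More than one rejection is wanted. Section 3.2, Hypothesis 1, reads "Each intervention will be superior to enhanced usual practice at increasing vaccine confidence", and Hypothesis 2 adds that the webinar beats the social media website. Section 4.6 gives the basis for the sample size: "LTCWs (600 per arm) provides 80% power to detect an 8% difference in the rate of scores above this threshold between groups". That calculation takes a two-sided error rate of 0.05, and it also claims 80% power for 10 points after 40% attrition. It does not mention the 0.016 cut.

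**The concern.** A single-step rule holds every test at 0.016 whatever the other two show. Once one null hypothesis has been rejected, at most two can still be true, so guarding against three false rejections is stricter than the stated family-wise error requires. The cost falls on the second and third claims: that the other intervention also beats usual practice, and that the two interventions differ. Section 3.2 hypothesises exactly these claims, so power is given up on them with no gain in error control.

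**Working it through.** **Inputs.** From the documents: three tests, two one-tailed and one two-tailed; family-wise error below 0.050; cut 0.016 (Appendix B); 600 per arm and 8 points, or 360 per arm (600 × 0.60) and 10 points (section 4.6). Assumed: control rate 20% to 50%, because none is given. Arm 1 versus Arm 2 is computed as a two-tailed test of difference, because no equivalence margin is given.

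**Step 1: the plan's own power.** Power = Φ((d − z·s0)/s1), with s0 = √(2p̄(1−p̄)/n) and s1 = √((p1(1−p1) + p3(1−p3))/n). At p3 = 0.35, p1 = 0.43, n = 600: s0 = 0.02816 and s1 = 0.02807. Then (0.08 − 1.96 × 0.02816)/0.02807 = 0.884, so power is 81.2%. The worst-case control rate (about 0.46) gives 79.2%, so the stated 80% is reproduced. For 360 per arm and 10 points, the results are 80.4% at a control rate of 0.30, 78.3% at 0.35 and 76.6% at worst. Control rates near 0.35 are compatible with both stated figures.

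**Step 2: the threshold.** 0.05/3 = 0.0167, cut to 0.016; 3 × 0.016 = 0.048, below 0.050. The z value for 0.016 is 2.144 one-tailed, which agrees with the stated 2.15. Two-tailed it is 2.409; the stated 2.45 corresponds to p = 0.0143. At one-tailed 0.016 the Step 1 case gives (0.08 − 2.144 × 0.02816)/0.02807 = 0.699, or 75.8% power.

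**Step 3: why Holm costs no error control.** Order the three p-values and compare them with α/3, α/2 and α, stopping at the first failure. Suppose m of the nulls are true. When Holm first rejects a true null, at most 3 − m rejections have come before it, so its p-value is at most α/m. By the Bonferroni inequality over the m true nulls, the chance of this is at most α, under any dependence. The first cut equals Bonferroni's and later cuts are larger, so no Bonferroni rejection is lost. With α = 0.048 the cuts are 0.016, 0.024 and 0.048, which keep the present total.

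**Step 4: size of the gain.** Simulation of the three z-tests, 200,000 trials per row, control rate 35%:

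| Effects (Arm 1 / Arm 2), n per arm | Quantity | Fixed 0.016 | Holm, total 0.048 | Holm, total 0.05 |
|---|---|---|---|---|
| none, 600 | any false rejection | 4.3% | 4.3% | 4.4% |
| +8 / +8, 600 | each superiority test | 75.4% | 78.8% | 79.4% |
| | both superior | 62.5% | 69.2% | 70.1% |
| | at least one win | 88.4% | 88.4% | 88.7% |
| +10 / +10, 360 | each superiority test | 72.3% | 76.0% | 76.7% |
| | both superior | 58.5% | 65.9% | 66.8% |
| | at least one win | 86.0% | 86.0% | 86.5% |
| +8 / +4, 600 | Arm 2 vs Arm 3 | 23.9% | 29.9% | 30.8% |
| | Arm 1 vs Arm 2 | 15.8% | 20.8% | 21.1% |
| +16 / +8, 600 | Arm 2 vs Arm 3 | 75.6% | 87.1% | 87.9% |
| | Arm 1 vs Arm 2 | 64.7% | 77.6% | 79.2% |

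Over control rates of 20% to 50%, with equal planned effects and the total kept at 0.048, the gain is about 2.5 to 4 points per superiority test and 5 to 8 points for both. The 0.05 version usually adds a point or less to this. At control rates of 45% to 50% and 600 per arm a check run put it somewhat higher, at about 5 and 9 points, because the first cut is also slightly looser and the statistic takes discrete values.

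**Step 5: the closed version.** If the null for Arm 1 versus Arm 2 is equality, any two nulls that include it imply the third. After one superiority win at 0.05/3, the other two tests may then use 0.05. In the +8 / +8 case this raises the power to show both superior to 78.6%. If that null is instead a difference of at least a margin, the implication fails. Simulated at 600 per arm with control rates of 30% to 50%, Arm 2 equal to control and Arm 1 above it by exactly an assumed margin, family-wise error under the closed rule was 5.5-5.8% (8 points), 6.9-7.3% (10 points) and 8.5-8.8% (15 points). Plain Holm stayed at or below 4.6%.

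**The case against.** The strongest reply is that nothing here is an error. Bonferroni is valid, and it makes decisions and simultaneous intervals agree, which matters because Appendix B decides by interval. That stands: Holm gives up the agreement, and a sponsor may reasonably value it.

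It is also true that the documents never define success as winning on both interventions. Section 4.8.2 compares each with control, and for at least one win Holm offers almost nothing.

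A reader might infer that Holm gives clearly more power throughout, or point to the rise from 65% to 79% for Arm 1 versus Arm 2. The documents do not support this. That rise needs a webinar effect of 16 points, twice the 8 points in section 4.6. With effects of 8 and 4 points the later tests gain about 5 to 9 points over the assumed control rates and remain poorly powered.

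A reader might also infer that the closed version is free. Section 4.8.2 and Appendix B call Arm 1 versus Arm 2 an equivalence analysis and give no margin. The two-proportion z-test, and the remark in section 4.8.2 that superiority, inferiority or no distinguishable difference would each be informative, suggest a test of difference, but the plan does not settle it. Plain Holm is valid either way, provided each p-value is valid.

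Finally, section 4.4.2 shows that data collection has begun, and section 4.7.4 leaves the team unblinded and the analyst blinded only where possible. A move to a more liberal rule therefore needs safeguards.

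**Conclusion.** The point holds as a matter of efficiency, not validity. Holm rejects whatever the fixed 0.016 rule rejects and keeps family-wise error below 0.05. With both interventions at the planned effect, the gain is modest per test and somewhat larger for showing both superior. It is close to nil for a first win. These sizes rest on the assumed control rates, on effects equal to those in section 4.6, and on treating Arm 1 versus Arm 2 as a two-tailed difference. That Holm rejects at least as much rests on none of these. The case for the closed version is conditional on how Arm 1 versus Arm 2 is defined.

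**What to change.** Before any outcome is seen by arm, amend the multiple-testing paragraph of Appendix B and record the change under section 5.2:

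- Order the three primary p-values and test at 0.05/3, 0.05/2 and 0.05 (or 0.016, 0.024 and 0.048 to keep the present total), stopping at the first failure.
- Base significance on these p-values. The 2.15 and 2.45 multipliers then no longer decide the result, and the mismatch between 2.45 and a 98.4% interval (2.41) should be corrected.
- Keep the 98.4% intervals for reporting only, and say that such an interval may occasionally include zero when Holm rejects.
- Use the closed version only if the SAP first states that Arm 1 versus Arm 2 is a two-sided test of difference and not an equivalence test with a margin. Otherwise leave it out.

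The cost is one paragraph, a dated amendment and the loss of exact agreement between intervals and decisions. No participants are added.
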